A Within Subjects Comparison of Two Antegrade Flushing Regimes in Children

NCT02435069

08/23/2019

This study was a part of a dissertation presented to the Graduate School of the University of Florida in partial fulfillment of the Doctor of Philosophy degree requirements.

Study design

This study compared two flushing regimens utilizing a cross-over design embedded in a single subject A-B-C-B'-C'-B1' design with subjects acting as their own control; thereby ensuring the highest possible degree of equivalence across treatment conditions and allowing greater precision and efficiency in estimates of treatment effects (Janosky, Leininger, Hoerger & Libkuman, 2009; Piantadosi, 2005; Portney & Watkins, 2009). In both methods subjects were randomized to treatment sequence decreasing the threat of order effects, increasing group equivalency in the cross-over design, minimizing variability in measurement due to subject or period differences, and increasing internal validity (Chow & Liu, 2014; Jones & Kenward, 2003). This study was well suited to single-subject repeated measures design, because children requiring an ACE procedure constitute a very small population with widely variable anatomic and physiologic causative factors making sample homogeneity difficult. The design allowed for frequency and volume adjustment of each flushing regimen as needed facilitating dose response comparison and aiding in identifying which flushing regimen required the minimal dose and administration frequency and had fewer side effects while achieving stool continence (Gast, 2010; Janosky et al., 2009; Kazdin, 2011). Subjects were limited to children who were scheduled for a cecostomy or appendicostomy ensuring a naïve gut to the effects of a flushing regimen and allowing for a true no-treatment baseline. Flush effects were reversible, making this intervention amenable to a withdrawal design. Specimen collection occurred after an active wash out period at the completion of each flushing regimen facilitating comparison of treatment effects on electrolytes and stool calprotectin, negating the possibility of carry-over effects.

Regulatory Considerations

The potential risks associated with this study conferred no greater than minimal risk as categorized by the National Institutes of Health (National Institutes of Health [NIH], 1998). However, it involved vulnerable subjects necessitating full Institutional Review Board (IRB) approval, legal guardian informed consent by at least one parent, and child assent for children age 7 and above (Knox & Burkhart, 2007; Pieper, 2008). In addition, although normal saline and USP glycerin have been used for over three decades in the clinical setting as ACE flushing solutions, administration of either solution through an ACE stoma is considered off-label use and therefore the study required FDA approval. Prior to submission to the IRB, the study design was reviewed by the Nemours Children's Clinic (NCC) Research Committee which made suggestions for revision but deferred to the investigator's Dissertation Committee for approval of study design and analysis. The UF IRB deferred to the NCC IRB because the study was to be completed at NCC. An IRB authorization agreement was completed, and the contract was signed by all parties. The proposal was submitted to the FDA and an IND was obtained. A Nemours Children's Clinic IRB application was completed. As a part of the NCC IRB application process, submissions for research involving investigational drugs and biologics and management of research pharmaceutical products were completed and approved. NCC IRB approval was obtained and renewed annually. Legal guardian informed consent and child assent for children 7 and above were obtained for each subject prior to the start of data collection.

Subjects

Subject characteristics' data were collected and included age in years and months, ethnicity, diagnosis, description of level of spinal cord lesion or anal-rectal malformation when appropriate, description of physical examination of anus, and the reason for undergoing an ACE procedure.

Setting

Following parental consent and child assent, baseline data were collected daily for a minimum of 2 weeks prior to surgery. Baseline data included the frequency of fecal soiling, and the frequency and severity of abdominal pain. Baseline blood sample for electrolytes and stool for calprotectin were obtained in the preoperative period. The baseline samples were collected prior to initiation of the preoperative bowel prep. Postoperatively, the child was randomly assigned to either start the saline or USP glycerin flush protocol. A clinician from the surgical division at NCC met with the parent and child in the immediate postoperative period for initiation of the first antegrade flush. At that time, the clinician reviewed the flush protocol in detail, including materials and procedures. The child received the first antegrade infusion during that hospital visit. A home visit was scheduled by the investigator for the initial antegrade flush following hospital discharge. Procedural reliability was ascertained by calculating procedural fidelity for each procedural variable to assure the intervention was accurately implemented in keeping with the methods section of the proposal. Procedural fidelity was ascertained prior to each regimen change during the clinic visit scheduled prior to each phase change.

Measures

Dependent variables collected at baseline were recorded daily and included the number of episodes of fecal soiling per day, the frequency and severity of abdominal pain measured using the Wong-Baker Faces Pain Rating Scale (WBFPRS) as the age-appropriate visual analog scale, serum electrolytes, and stool for calprotectin. The WBFPRS scale ranges from 0 (very happy without pain) to 10 (the worst pain imaginable). The WBFPRS has undergone extensive testing and has well established psychometrics in children (Tomlinson, von Baeyer, Stinson, & Sung, 2010; Wong & Baker, 1988).

Dependent variables collected postoperatively were obtained daily throughout all phases of the dosing and maintenance phases and included the number of episodes of fecal soiling per day, frequency and severity of abdominal pain and pain associated with antegrade flush administration measured using the WBFPRS as the age appropriate visual analog, and the presence of flush associated vagal symptoms. Serum electrolytes and stool for were calprotectin collected at the end of each dosing phase. Total flush volume was recorded with each flush and measured in mL. Direct parental observation with event recording was used to track and tally soiling episodes defined as non-toilet elimination. Dependent variables were measured and recorded by the parent using a data collection sheet specifically designed for this study. The parent was requested to call if the child was having accidents, discomfort greater than a 4 on the WBFPRS associated with the antegrade flush, or vagal symptoms. The investigator documented any event that could potentially cause a change in level, stability, or trend of the dependent variable not related to the intervention (i.e. initiation of antibiotics or an intercurrent illness).

Materials

Each child had a low-profile button in place to ease flush administration. A cabinet was identified in the clinic space for storage of the flushing solution with continuous temperature monitoring using a MCC

USB 501-LCD thermometer. The cabinet was locked with restricted key access. The temperature in the storage cabinet was consistently maintained between 15 and 30 degrees Centigrade. A temperature monitoring log was completed daily. No ambient temperature excursions occurred. Flush solution type, volume dispensed, lot numbers, and flush solution dispensing time and date were recorded in a dispensing log.

High Volume Flush

Each child had a low-profile button in place to ease flush administration. The normal saline was infused using a 1,000 mL enteral feeding bag with drip chamber and roller clamp hung from an IV pole or a hook on the bathroom wall located 5 feet above the toilet seat. Enteral feeding bag tubing and the low-profile device access tubing was primed with the high-volume flush prior to connecting the access tubing to the low-profile device and initiating the flush infusion. Step by step procedural directions were reviewed verbally with the parents and were reinforced through the provision of written instructions located in a parent notebook. The written procedure served as a check-off list to document procedural integrity which was checked during the initial home visit and each clinic visit scheduled with every change in flush solution and change in phase.

Low Volume Flush

Each child had a low-profile button in place to ease flush administration. For the low volume flush, room temperature USP glycerin was mixed with room temperature normal saline in a calibrated six-ounce plastic container with a screw top and subsequently poured into a 60 mL catheter-tipped syringe attached to the low-profile device access tubing. The tubing was primed and connected to the low-profile device. The syringe containing flush solution was held at the child's shoulder level while the flush solution infused. Following flush completion, the tubing and bag or syringe were washed in warm soapy water, thoroughly rinsed, and allowed to air dry. Step by step written procedural directions were included in a parent notebook and served both as procedural reinforcement and as a check-off list to document procedural integrity which was checked during the initial home visit and with each subsequent scheduled clinic visit completed with every change in flush solution and every change in phase.

Procedures

Randomization to one of the two treatment sequences occurred in the immediate postoperative period using restricted random assignment to force equal sample size and was accomplished using the SAS random number generator.

High Volume Regimen

The high-volume regimen consisted of normal saline flush at a starting dose of 10mL/kg infused every other day and adjusted by flush volume and frequency of administration until stability of target outcomes was achieved. Notification of any fecal soiling resulted in an additional 5 mL/kg volume adjustment with a subsequent increase in administration frequency, if needed, so as not to exceed a maximum dose of 500 mL administered daily for a child under five years of age and 1000 mL administered daily for a child over 5 years of age. If the child could not achieve continence on the maximum dose and had not been trialed on the alternate therapy, they were trialed on USP glycerin but did not proceed to the maintenance phase of the study. If the child experienced side effects greater

than 4 on the WBFPRS at the starting saline dose, flush volume was incrementally decreased as needed by 2.5 mL/kg to the lowest dose of 5 mL/kg. The goal of the dosing phase was to identify the lowest effective dose and flushing frequency that resulted in continence with minimal side effects. If the dose required to minimize side effects resulted in fecal soiling or the child had side effects greater than 4 on the WBFPRS at the lowest flush dose, and had not been trialed on the alternate therapy, they were trialed on USP glycerin but did not proceed to the maintenance phase of the study.

Low Volume Regimen

The low volume regimen consisted of USP glycerin diluted in normal saline instilled through the low-profile device starting on a dose of 20 mL of USP glycerin mixed in >20 mL of saline and adjusted by flush volume and frequency of administration until stability of target outcomes was achieved. The saline served as a diluent and was mixed at a sufficient dose to allow easy infusion of the solution through the ACE access tubing. Notification of any fecal soiling resulted in the addition of 5 to 10 mL with subsequent increase in frequency of administration, if needed, so as not to exceed 50 mL of USP glycerin administered daily. If the child could not achieve continence on the maximum dose and had not been trialed on the alternate therapy, they were trialed on high volume normal saline but did not proceed to the maintenance phase of the study. If the child experienced side effects greater than 4 on the WBFPRS at the starting USP glycerin dose, flush volume was incrementally decreased as needed by 5 mL increments to the lowest dose of 5 mL. The goal of the dosing phase was to identify the lowest effective dose and flushing frequency that resulted in continence with minimal side effects. If the dose required to minimize side effects resulted in fecal soiling or the child had side effects greater than 4 on the WBFPRS at the lowest flush dose, and had not been trialed on the alternate therapy, they were trialed on normal saline but did not proceed to the maintenance phase of the study.

Optimal Dose Regimen

Following optimal dose determination, the child was maintained on that volume and administration frequency for at least 2 weeks. A clinic visit was scheduled once the above criteria had been met. At that visit, the child was flushed at the optimal dose, labs were drawn, a stool sample collected, the procedure for the next regimen was reviewed with the parent and child, and procedural fidelity was ascertained.

Regimen Maintenance Phase

Following successful completion of the dose-response phase, patients were randomized for a second time to either a saline-glycerin-saline or a glycerin-saline-glycerin sequence. The maintenance phase of the study began by administering the established effective dose and frequency of administration for the first flush in the sequence. The child remained on treatment for 4 weeks. The treatment was withdrawn. The child was subsequently placed on the next treatment in the sequence at the pre-established effective dose and frequency for 4 weeks. The second flush was then withdrawn and the initial flush in the sequence was reintroduced for an additional two weeks. If the child experienced recurrence of fecal incontinence or discomfort greater than a 4 on the pain scale, they were dropped from the study. If they successfully completed the maintenance phase, the child was placed on the flushing regimen of his/her choice at the dose and frequency of administration that maintained continence.

Specimen Collection

A stool sample for calprotectin was obtained during the baseline phase prior to any pre-operative bowel prep and additional stool samples were obtained at the completion of each dosing phase for a total of 3 samples. Blood samples for electrolytes were drawn preoperatively and postoperatively at the end of each dosing phase at the time stool samples were obtained for a total of three samples. Funding was secured. Accounts were set up with an outside lab for processing blood samples for electrolyte determination and a second outside lab for processing stool samples for calprotectin.

Statistical Analysis

This study was a within subjects design with all subjects demonstrating consistent fecal incontinence at baseline and sufficient intervention and post-intervention data points to allow for time series analysis. Data points were graphed on an equal interval 2:3 ratio ordinate and abscissa scale line graph to prevent data distortion during visual analysis. Dependent measures were graphed on the ordinate scale with time-by-day graphed on the abscissa scale. Independent variable effects on target behaviors were analyzed using well established single-case methodology (Gast, 2010; Hartmann et al., 1980; Ma, 2006; Kazdin, 2011; Portney & Watkins, 2009). Clinicaltrials.gov is not configured to allow reporting outcomes from most methods of within subjects data analysis. Reported data was limited to the results from numeric descriptive and inferential analysis that could be adapted to the Clinicaltrials.gov format.

In addition to single-case analytic methodology, descriptive and inferential analysis was used to compare interventional effects and increase the reliability of visual methods analysis. Both the dosing and maintenance phase of the study constituted a 2-treatment crossover design with each child receiving both treatments in both interventional phases of the study (Portney & Watkins, 2009). Descriptive statistics included mean, median, range and standard deviation. A cross-over design compares two treatment sequences; therefore, the groups are independent (Chow & Liu, 2014). Of concern, carry over and direct-by-period interaction is a potential confound with cross-over designs, which if present, could bias treatment effects (Jones & Kenward, 2003; Senn, 2002; Shuster, 2007). The decision was made to use a two-tailed, two-sample pooled variance t-test to lend precision in the presence of carry over effects, and precision and accuracy in the presence of unequal sample size (Shuster, 2009). Significance level was set a priori at 0.05. Effect size was used to determine the magnitude of the treatment difference (Polit, 2010; Rempher & Silkman, 2007).

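### The titration rules yield the first effective dose and frequency on a ladder; for children never tried lower, this is only an upper bound on the lowest effective one

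*Combined protocol and SAP*

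**What the plan says.** Saline starts at 10 mL/kg every other day (High Volume Regimen). Glycerin starts at 20 mL in more than 20 mL of saline, with no starting frequency stated (Low Volume Regimen). Each regimen is then "adjusted by flush volume and frequency of administration until stability of target outcomes was achieved". The specific moves written down are:

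- **Saline up.** Notified soiling "resulted in an additional 5 mL/kg volume adjustment with a subsequent increase in administration frequency, if needed", to a cap of 500 mL daily under five years and 1000 mL daily over five.
- **Glycerin up.** "Notification of any fecal soiling resulted in the addition of 5 to 10 mL with subsequent increase in frequency of administration, if needed", to a cap of 50 mL of glycerin daily.
- **Saline down.** For side effects above 4 on the WBFPRS at the starting dose, "flush volume was incrementally decreased as needed by 2.5 mL/kg to the lowest dose of 5 mL/kg".
- **Glycerin down.** "If the child experienced side effects greater than 4 on the WBFPRS at the starting USP glycerin dose", then "flush volume was incrementally decreased as needed by 5 mL increments to the lowest dose of 5 mL".

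The Optimal Dose Regimen section holds the resulting volume and frequency for at least 2 weeks, and the Regimen Maintenance Phase section carries them forward. Both regimen sections state the purpose: "The goal of the dosing phase was to identify the lowest effective dose and flushing frequency that resulted in continence with minimal side effects". The Study design section describes the adjustable dosing as "facilitating dose response comparison and aiding in identifying which flushing regimen required the minimal dose and administration frequency".

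**The concern.** A dose is shown to be the lowest effective one only if something lower was tried and failed. The written rules create that evidence for a child who soils and is raised. They do not create it for a child who does well at the start, because nothing triggers a reduction and the stopping condition is already met. For that child the recorded value is set by where the protocol chose to begin.

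At stake is the claim about which regimen needs less, and less often. A clinician or family would take a reported lowest effective dose as a tested minimum. The Statistical Analysis section lists means and standard deviations among its descriptive statistics and does not name dose or volume. Nothing in the plan therefore stops bounded values from being averaged as if they were exact.

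**Working it through.** The plan gives no figure of its own to reproduce. All inputs are the starting doses, steps and floors listed above. One assumption is made: more volume never worsens continence.

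**1. What each path through the rules shows**

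| Path | Volume | Frequency |
|---|---|---|
| Stayed at the start | Upper bound: nothing lower tried | Upper bound |
| Stepped down for pain | Upper bound: stopped at the first tolerated volume that kept continence | Upper bound |
| Raised in volume only | Bracketed between last failing and first effective volume, at the starting frequency | Upper bound: no lower frequency tried at the new volume |
| Raised in volume, then frequency | Lower volumes untried at the final frequency | Bracketed: the lower frequency failed at the final volume |

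**2. Size for a child who stays at the start** (starting dose ÷ protocol floor)

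- Saline: 10 ÷ 5 = 2.0. The 7.5 and 5 mL/kg rungs are untried.
- Glycerin component: 20 ÷ 5 = 4.0. The 15, 10 and 5 mL rungs are untried.
- The 4.0 applies to the glycerin component only. If the diluent were kept at 20 mL, total flush volume would give (20 + 20) ÷ (5 + 20) = 1.6, and less with more diluent.

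**3. Size for a child stepped down but above the floor**

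- Saline stopped at 7.5 mL/kg: 7.5 ÷ 5 = 1.5.
- Glycerin stopped at 15 or 10 mL: 15 ÷ 5 = 3.0, or 10 ÷ 5 = 2.0.

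**4. A child raised in volume only.** The rung below failed, so the excess over the true minimum volume at that frequency is less than one step: under 5 mL/kg for saline, and under 5 to 10 mL for glycerin.

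**5. Frequency.** Every other day is 7 ÷ 2 = 3.5 saline flushes a week. No lower schedule and no frequency floor is written, so no ratio can be computed. For glycerin even the starting value is unstated.

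**6. Effect on a between-regimen comparison.** Take a child of *w* kg continent and comfortable at both starting doses. The assigned saline-to-glycerin volume ratio is 10*w* ÷ 20 = *w*/2, whatever the child's true needs. The ratio of true minima within the protocol's range could lie anywhere from 5*w* ÷ 20 = *w*/4 to 10*w* ÷ 5 = 2*w*, which is 0.5 to 4 times the assigned ratio. At an assumed 20 kg the assigned ratio is 10 and the possible range is 5 to 40.

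**The case against.** The best defence is that the general adjustment clause has no stated direction, that the Study design section allows adjustment as needed, and that the goal sentence implies reductions. Starting low, raising on failure and stopping at the first success is also an ordinary meaning of titrating to the lowest effective dose. The minimal-dose aim is worded cautiously, no test of it is planned, and the maintenance phase relies only on an established effective dose. Daily graphs and descriptive statistics are planned and come close to a per-child display.

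Part of this stands. Reductions may have been made that were not written down, and any child who had one should be exempt. The defence does not remove the gap, though. Where the protocol wanted a reduction it wrote the trigger, the step and the floor, and it wrote none for a comfortable, continent child. The ordinary titration meaning also sits badly with a protocol whose own range extends below the starting dose.

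Three stronger readings are tempting, and the documents do not support them:

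- *Every recorded dose is overstated.* A child raised in volume has a bracketed volume, and a child raised in frequency has a bracketed frequency at the final volume.
- *The 5 mL glycerin floor means total flush volume*, which would enlarge the overstatement. That conflicts with a diluent of more than 20 mL, and the reduction starts from the glycerin dose.
- *The crossover comparison itself is undermined.* Both regimens are compared at doses shown to give continence, and that does not require the doses to be minimal.

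**Conclusion.** The point holds in limited form. For children who stayed at the start or were stepped down for pain, the volume called optimal is only an upper bound on the lowest effective volume. The 2.0-fold and 4.0-fold figures are limits within the protocol's own range, not estimates of a typical error. Frequency is an upper bound for every child in whom it was not raised, including those who succeeded on a volume step. For a child whose frequency was raised, the remaining gap is that lower volumes were untried at that frequency.

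This rests on the rules as written and on more volume never worsening continence. The documents do not say how many children followed each path, so the practical effect cannot be sized. What changes is the lowest or minimal label and any ranking of the regimens built on it.

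**What to change.** Change the reporting only; no dosing rule is proposed.

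1. Call the dosing-phase result the first effective dose and frequency on the titration ladder, not the lowest effective or minimal dose.
2. Give a per-child table. Mark volume ≤ for children who stayed at the start (≤10 mL/kg saline, ≤20 mL glycerin) or were stepped down. Mark frequency ≤ for children whose frequency was not raised. Give the counts for each regimen.
3. For children whose frequency was raised, note that lower volumes were untried at the final frequency.
4. Give no mean or standard deviation of dose or frequency that treats bounded values as exact, and draw no between-regimen conclusion on minimal dose or frequency from them.
5. If a reduction was tried outside the written rules, say so and exempt that child. State the glycerin starting frequency.

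The cost is wording and re-tabulation. The Measures section says total volume was recorded with each flush, so the dose path needs no new data. If glycerin cannot be separated from diluent in those records, use the prescribed glycerin dose or say that it is unavailable. The downside is a more modest claim about minimal dose.

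### Do the specimen rules leave children who fail a regimen unsampled, or let flush fluid distort the stool calprotectin comparison?

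*Combined protocol and SAP*

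**What the plan says.** All sections are in the combined protocol and SAP.

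- **Measures** gives a general rule: "Serum electrolytes and stool for were calprotectin collected at the end of each dosing phase".
- **Specimen Collection** repeats it for stool: "additional stool samples were obtained at the completion of each dosing phase for a total of 3 samples". Blood is drawn at the same times, also three in all. Neither section makes sampling depend on the regimen having worked.
- **Optimal Dose Regimen** describes a visit after the optimal dose has been held for at least 2 weeks: "A clinic visit was scheduled once the above criteria had been met". What happens there is listed as: "At that visit, the child was flushed at the optimal dose, labs were drawn, a stool sample collected".
- **High Volume Regimen** covers a child who fails on saline and has not yet had the other flush: "they were trialed on USP glycerin but did not proceed to the maintenance phase of the study". **Low Volume Regimen** has the mirror rule. Neither mentions specimens.
- **Setting** and **High Volume Flush** provide a clinic visit at each change of phase or solution, described there for procedural checks. **Setting** also places baseline specimens before the bowel preparation.
- **Study design** says: "Specimen collection occurred after an active wash out period at the completion of each flushing regimen". The wash-out is not defined.
- **Statistical Analysis** describes "each child receiving both treatments in both interventional phases of the study".

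**The concern.** Two things catch the eye.

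First, the only step-by-step account of a post-treatment specimen visit is triggered by success. If it is the only occasion for sampling, a child who fails a regimen gives no specimen for it. The comparison of electrolytes and calprotectin would then describe only children who did well on each regimen.

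Second, the list puts the flush ahead of the stool and gives no interval. Calprotectin is a concentration, the two regimens use different volumes, and baseline stool precedes any flush. A difference between regimens, or from baseline, could then partly reflect dilution. A wash-out of the earlier regimen would not remove fluid from a flush given at the same visit.

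**Working it through.** **1. Specimen count.** Inputs: one baseline specimen (Setting, Specimen Collection) and two dosing phases, one per regimen. 1 + 2 = 3, which reproduces the stated total for stool and for blood. Under success-only sampling a child would have 3, 2 or 1 specimens after 0, 1 or 2 failed regimens. The stated total fits the general rule for every child. It fits success-only sampling only for children who succeeded on both regimens.

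**2. The sections side by side.** Measures and Specimen Collection state when specimens are taken, without a condition. Optimal Dose Regimen describes the visit of a child who reached a stable dose; it does not say that specimens are taken only there. The failure rules say which flush comes next and are silent on specimens, so the general rule applies. A visit at each change of solution supplies an occasion. If the Statistical Analysis sentence about each child receiving both treatments in both phases reports what happened, no child failed dosing and the group is empty. If it describes the design, it does not settle the matter.

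**3. Size of any selection.** Suppose a share *f* of children fail a regimen unsampled and their mean differs from that of the successes by *d* SD. That regimen's mean then shifts by *f × d*. With assumed values:

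- f = 0: 0
- f = 0.10, d = 0.5: 0.10 × 0.5 = 0.05 SD
- f = 0.30, d = 1: 0.30 × 1 = 0.30 SD

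This is the shift in one regimen's mean, whereas the design compares regimens within a child. If a share *p* of children lack a saline–glycerin pair, the mean difference among complete pairs departs from that of all children by *p × (D_pair − D_nopair)*, where *D* is the mean saline-minus-glycerin difference in each group. This is zero when the two groups have the same difference, however large *d* is. Assuming independent failure of 5% to 30% per regimen, complete pairs fall to 0.95² = 90% or 0.70² = 49% of children. The documents give neither a failure rate nor any value of *D*.

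**4. Size of any dilution.** Assume 100 g of stool, equal mucosal output under both regimens, and a share *m* of the flush mixed into the sample. Then

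saline reading / glycerin reading = (100 + m × mix) / (100 + m × saline).

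Starting volumes are 10 mL/kg for saline (High Volume Regimen) and 20 mL glycerin in more than 20 mL saline, so above 40 mL (Low Volume Regimen). The upper bound used for the mix is the capacity of the container in Low Volume Flush ("mixed with room temperature normal saline in a calibrated six-ounce plastic container with a screw top"), about 177 mL.

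| Weight (assumed) | Saline | Mix | m | Ratio | Saline reading |
|---|---|---|---|---|---|
| 20 kg | 200 mL | 40 mL | 1 | 140/300 = 0.467 | 53% lower |
| 20 kg | 200 mL | 40 mL | 0.25 | 110/150 = 0.733 | 27% lower |
| 20 kg | 200 mL | 177 mL | 1 | 277/300 = 0.923 | 8% lower |
| 20 kg | 200 mL | 177 mL | 0.25 | 144.25/150 = 0.962 | 4% lower |
| 10 kg | 100 mL | 40 mL | 1 | 140/200 = 0.700 | 30% lower |
| 10 kg | 100 mL | 177 mL | 1 | 277/200 = 1.385 | 39% higher |
| any | any | any | 0 | 1.000 | no difference |

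With 177 mL of mix the direction reverses below 177/10 = 17.7 kg.

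These figures illustrate a mechanism and do not estimate the effect at the specimen visit:

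- They use starting doses, whereas the child was flushed at the optimal dose. Under the stated limits a 20 kg child over five could be on anything from 5 × 20 = 100 mL to 1000 mL of saline.
- 177 mL is what the container holds. Filling it at the starting dose would need 177 − 20 = 157 mL of diluent, which no section prescribes.
- Stool mass, body weight and mixing are all assumed.

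**5. Wash-out.** If it means the period of at least 2 weeks on the new regimen, it agrees with Optimal Dose Regimen and concerns carry-over from the earlier regimen. If it means a flush-free interval, it conflicts with a flush at the specimen visit. The first reading makes the sections consistent. On either reading, nothing here shows that carry-over occurred.

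**The case for a change.** The strongest contrary case is that Optimal Dose Regimen is the only operational account of sampling and depends on success, while the visits at a change of solution are described for procedural checks only. They show that failures could have been sampled, not that they were. A child who fails the second regimen has no further change of solution, so no such visit is named. The Statistical Analysis sentence cannot be literally true of a child who never entered maintenance. On stool, the flush is listed first, no section excludes flush fluid, and with one post-treatment specimen per regimen no repeat sample would expose a timing artefact.

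Part of this stands. The documents do not confirm that every failed regimen was sampled, they leave the flush-to-stool order and interval open, and the wash-out is undefined. But silence in the failure rules does not override a general rule stated in two sections, and the order of items in a sentence is weak evidence of the order of events.

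The available remedies add little. Sampling after every regimen is already the rule. Fixing the time of the blood draw answers no problem shown for blood. Stool taken before the flush would be free of that flush's fluid, but may be hard to obtain in children managed by flushes and may need home collection. That could exchange a possible dilution for missing specimens.

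**Conclusion.** No change to the plan follows. On who is sampled, the sections are compatible: a general rule covers every dosing phase, and one section describes the visit of a child who succeeded. On timing, there is a genuine but small gap in detail. Its effect on calprotectin cannot be calculated from the documents, and the illustrative range of 53% lower to 39% higher includes zero and rests on assumed stool mass, weight, mixing and volumes. The selection figures of 0 to 0.30 SD rest on assumed failure rates and differences, and do not measure bias in the within-child comparison.

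The study is complete, so the gap is one the analyst can fill when reporting: the number of children sampled per regimen, including any who failed it; what the wash-out was; and the order and interval of flush and stool, or that these were not recorded. If stool did follow the flush, possible unequal dilution is a limitation to mention beside the calprotectin result. This conclusion assumes that the Specimen Collection rule was applied as written.
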